15.1.1 All Adverse Events

Adverse events will be summarized by worst severity per subject, using MedDRA version 22.0 (or above) preferred term as event category and MedDRA 22.0 (or above) primary system organ class (SOC) body term as Body System category.

Adverse events summaries will be ordered alphabetically for SOC, and PT within SOC unless otherwise specified.

With respect to TEAEs by severity, subjects will be counted only once for multiple events in the same SOC, by worst severity experienced. If a subject experiences more than one TEAE within a PT, he/she will be counted only once in the PT for the greatest severity he/she experienced. If severity is missing for an event, the greatest severity will be assumed.

With respect to TEAEs by relationship to IMP, subjects will be counted only once for multiple events in the same SOC, by strongest/closest relationship with IP. If a subject experiences more than one TEAE within a PT, he/she will be counted only once in the PT for the strongest relationship to IP he/she experienced. If relationship to study treatment is missing for an event, the strongest relationship will be assumed.

Adverse events related to trial treatment are those events with relationship missing, unknown or yes.

In case a subject had events with missing and non-missing grades, the maximum of the non-missing grades will be displayed.

Treatment refers to the following trial treatments administered: Biltricide® or L-PZQ ODT; and includes the overall/total group. The following overall frequency tables will be prepared. In addition, the tables will be provided by PT and primary SOC in alphabetical order, unless otherwise specified:

- TEAEs by treatment group
- TEAEs by treatment group and severity
- Related TEAEs by treatment group
- Related TEAEs by treatment group and severity
- TESAEs by treatment group
- TESAEs by treatment group and severity
- Related TESAEs by treatment group
- Related TESAEs by treatment group and severity
- Most commonly reported AEs by PT, sorted by overall frequency

The following listings will be also be prepared:

- TEAEs leading to subject withdrawal
- TEAEs leading to death

Clinical trial.gov and EudraCT -requirements

The following summary tables for non-serious adverse events (excluding SAEs) applying frequency threshold of 5% will be provided.

- TEAEs by treatment group
- Related TEAEs by treatment group

In all adverse events tables Treatment groups 1a and 1b will be presented as separate columns.

15.1.2 Adverse Events Leading to Study Intervention Discontinuation

All AEs leading to treatment discontinuation will be listed by SOC and PT.

15.2 Deaths, Other Serious Adverse Events, and Other Significant Adverse Events

15.2.1 Deaths

In case a subject dies during the study, “Death” will be recorded as the “Primary reason for not completing” on eCRF page “End of Study” and a corresponding SAE will be recorded on the eCRF with outcome “FATAL”. Date and cause of death will be provided in individual subject data listing together with all dosing information, by cohort.

15.2.2 Serious Adverse Events

Tables will be provided by PT and primary SOC in alphabetical order:

- TESAEs by treatment group
- TESAEs by treatment group and severity
- Related TESAEs by treatment group
- Related TESAEs by treatment group and severity

In addition, listings will be provided of all SAEs.

15.3 Clinical Laboratory Evaluation

Laboratory values (including corresponding normal ranges) will be used for summary statistics and shift tables.

Quantitative data will be examined for trends using descriptive statistics (mean, SD, median, Q1, Q3, minimum, and maximum) of actual values and changes from baseline to each visit over time. The changes computed will be the differences from baseline (Day -7 to Day 1 samples(screening)) to end-of-treatment (Day 1 12hrs sample / early withdrawal). Qualitative data based on reference ranges will be described according to the categories (i.e. Low, Normal, High). Only the ‘high’ and ‘low’ categories will be flagged. The number of subjects with clinical laboratory values below, within, or above normal ranges will be tabulated for each test by treatment group. Shift tables of baseline versus end-of-treatment will be presented.

Laboratory values that are outside the normal range will also be flagged in the data listings, along with corresponding normal ranges. Any out-of-range values that are identified by the investigator as being clinically significant will be shown in a data listing.

Baseline (Day -7 to Day 1 samples(screening)) is the last measurement prior to the dose of any trial treatment.

Subjects without post baseline laboratory samples will be excluded from analyses with respect to change from baseline summaries.

Data will also be presented for absolute and change from baseline results using boxplots, by time point/visit.

Note: In order for summarization, quantitative clinical laboratory measurements reported as “ $<X$ ”, i.e. below limit of quantitation, will be converted to $X/2$, i.e. half value of the lower limit of quantitation; quantitative clinical laboratory measurements reported as “ $>X$ ” i.e. above the upper limit of quantification, will be converted by as $1.5X$, i.e. 1.5 folds of upper limit of quantification.

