| Section 4.4 End of Study Definition                               | End of study definition was updated to include the Extended Follow-up visit   | Alignment of text regarding end of study due to addition of the Extended Follow-up visit for Cohort 4  |
| Section 5.2 Exclusion Criteria                                    | 
Alignment of exclusion criteria between the Kenya and Ivory Coast protocols by removing the following exclusion criteria listed in the Ivory Coast protocol:
 
 
Marked increases of the liver enzymes: alanine aminotransferase and/or aspartate aminotransferase above 3 times the upper limit of normal (ULN); total bilirubin level above 1.5 times the ULN
 
Participants with hepatosplenic schistosomiasis
 
 | Harmonization of the Kenya and Ivory Coast protocols   |

| Section # and Name  | Description of Change   | Brief Rationale   |
|---|---|---|
| Section 5.4
Screen Failures                              | 
Clarification of the handling of participants not eligible for enrollment due to a temporary exclusion criterion.
 
Addition of text regarding blood sampling volume restrictions
 | The text was added due to a request from the Pharmacy and Poisons Board of Kenya.   |
| Section 6.5.1
Rescue Medicine                            | The word “schistosomiasis” was added to explicitly state the infection type   | Text added for clarification  |
| Section 8 Study Assessment and Procedures, Follow-up visits | 
Addition of the Extended Follow-up visit (Day 35 to 40)
 
The Rapid Diagnostic Test (RDT) may now be performed at the discretion of the Investigator for Ivory Coast sites.
       | 
Alignment of text regarding end of study due to addition of the Extended Follow-up visit.
 
Harmonization of the Kenya and Ivory Coast protocols
  |
| Section 8.5
Pharmacokinetics                             | 
Update the number of subjects with PK sampling to a total of 30 for the haematobium arm (Cohort 4)
 
Include PK sampling for up to 15 subjects in Group 1b (Biltricide).
          | 
The text was modified to address the PK sampling after a dose increase to 60 mg/kg for the Haematobium arm.
 
The text was modified due to the inclusion of PK sampling in the Biltricide control arm
 |

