PZQ is contraindicated in individuals with a history of proven hypersensitivity to PZQ or any of the excipients; in intraocular cysticercosis; and in combination with rifampicin. Caution is warranted in decompensated hepatic insufficiency or in patients with hepatosplenic schistosomiasis. Those with cardiac arrhythmias should be monitored during therapy. The same applies to patients with heart failure requiring digitalis therapy, since a digitalis-antagonistic effect has been demonstrated in animal studies.

The cumulative post authorization exposure to PZQ since January 2009 to May 2017 is estimated to be about 972,535 patients (Development Safety Update Report, reporting period 26 May 2016 to 25 May 2017).

More detailed information about the known and expected benefits and risks and reasonably expected AEs following administration of the L-PZQ ODT may be found in Section 4.2 (Scientific Rationale for Study Design) and the IB. Based on the available nonclinical and clinical data to date, the conduct of the study, as specified in this protocol, is considered justifiable.

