#### **Medical Conditions**

1. Findings in the clinical examination and/or laboratory safety examination on the treatment day, that in the opinion of the Investigator constitute a risk or a contraindication for the child's participation in the study or that could interfere with the study objectives, conduct or evaluation. This includes but is not restricted to bacterial or viral infections, such as dysentery, gastroenteritis, ascites, jaundice, etc
2. Participants with seizures and/or medical history of seizures and/or other signs of potential central nervous system involvement
3. Participants with known cysticercosis, or with signs or symptoms (e.g., subcutaneous nodules) suggestive of cysticercosis
4. Participants with an acute infection or other acute illness within the 7 days prior to study screening
5. Debilitating illness such as tuberculosis, malnutrition, etc

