### **8.2.1 Post Marketing Adverse Event Reports for PZQ**

Additional AEs reported from worldwide post-marketing experience and from publications with PZQ include: abdominal pain, allergic reaction (generalized hypersensitivity, including polyserositis), anorexia, arrhythmia (including bradycardia, ectopic rhythms, ventricular fibrillation, atrioventricular blocks), asthenia, bloody diarrhea, convulsion, eosinophilia, fatigue, myalgia, pruritus, rash, somnolence, vertigo and vomiting. For further details refer to the Biltricide® Summary of Product Characteristics (SmPC).

**Table 2** Known Adverse Reactions to PZQ

| Organ class                                     | Common
$\geq 1/100$ to $< 1/10$                | Very rare
$< 1/10,000$   | Not known  |
|---|---|---|--|
| Cardiac disorders                               |   | Unspecific arrhythmia   |  |
| Gastrointestinal disorders                      | Abdominal pain
Nausea
Emesis                |   |  |
| General disorders and administration conditions | Weakness
Fatigue
Increased body temperature |   |  |
| Hepatobiliary disorders                         |   | Hepatic coma (depending on the type of parasite in advanced disease stages) |  |
| Metabolism and nutrition disorders              | Lack of appetite                                  |   |  |
| Nervous system disorders                        | Headache
Dizziness
Lightheadedness          |   | Convulsions
(After the intake of PZQ for treating tapeworm infection, convulsions have occurred in rare individual cases; these have proven to be a reaction to co-existing neurocysticercosis. Such cases, which may occur especially in endemic regions of Taenia solium ( Cysticercus cellulosae ), should be clarified as quickly as possible.) |
| Skin and subcutaneous tissue disorders          | Urticaria   |   |  |

The completed Phase I studies (MS200585-001 and MS200661-001) confirmed the established good safety profile for the PZQ ODTs in healthy volunteers. No SAEs were reported, and no new types of treatment related AEs were observed. The following TEAEs occurred: abdominal

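### The Low/Normal/High laboratory shift tables cannot show liver worsening in a child already High at baseline, and no planned table counts such children or scales the change to the local upper limit

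*SAP*

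**What the plan says.** **Eligibility.** Protocol Section 5.2 contains no ALT, AST, bilirubin or hepatosplenic criterion. The amendment summary for version 1.2 explains the background: "Alignment of exclusion criteria between the Kenya and Ivory Coast protocols by removing the following exclusion criteria listed in the Ivory Coast protocol". The criteria concerned were "Marked increases of the liver enzymes: alanine aminotransferase and/or aspartate aminotransferase above 3 times the upper limit of normal (ULN", total bilirubin above 1.5 times the ULN, and "Participants with hepatosplenic schistosomiasis". Exclusion 1 remains. It covers treatment-day clinical or laboratory findings "that in the opinion of the Investigator constitute a risk or a contraindication for the child's participation in the study", and its examples include ascites and jaundice.

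**The liver as an area of caution.** Protocol 2.3 states: "Caution is warranted in decompensated hepatic insufficiency or in patients with hepatosplenic schistosomiasis". Table 2 in Section 8.2.1 lists hepatic coma as a very rare reaction in advanced disease.

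**Data collected.** Table 7 (Appendix 5) includes ALT, AST and bilirubin. Section 8 and the Schedule of Activities place the safety laboratory tests at screening and 12 hours after dosing. Section 8.2.4 has the local laboratory run them and requires its normal ranges to be sent to the sponsor.

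**Analysis.** SAP 15.3 specifies: "Qualitative data based on reference ranges will be described according to the categories (i.e. Low, Normal, High". Counts below, within and above range are tabulated by treatment group, and shift tables compare baseline with the 12-hour or early-withdrawal sample. The same section plans mean, SD, median, quartiles, minimum and maximum of values and of changes. It also plans boxplots of both, listings that flag out-of-range values next to their normal ranges, and a listing of values that the investigator calls clinically significant. Protocol 9.4.2 adds a by-subject, by-time-point listing of all safety values.

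**The concern.** A three-level scale has one level above the reference range. A child who starts there has nowhere further up to go, so the shift table cannot record deterioration, however large. These are also the children in whom any hepatic effect would matter most, given the caution in Protocol 2.3. Their presence is plausible: Protocol 2.3 reports that the one severe drug-related event in Phase II Part 1 had, among its alternative explanations, hepatic fibrosis from chronic hepatosplenic schistosomiasis.

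What is at stake is how the tables are read. A shift table without Normal-to-High movements is easily summarised as showing no hepatic signal. That statement would cover only children who began at or below the upper limit. A reader wanting the same answer for the others would have to pair values from listings, divide by each local ULN and count by hand.

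**Working it through.** The documents give no figure on this point, so there is none to reproduce. The check applies the SAP 15.3 rules to assumed ALT values in multiples of ULN.

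**Inputs.**
- From the documents: planned group sizes of 30 (Cohort 2), 50 (group 1b) and 100 (group 1a).
- Assumed for illustration: one child worsens, and all others stay at 0.6 x ULN at both times. A value above 1 x ULN is High.

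**Step 1: what the shift table shows.**

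| Baseline to 12 h (x ULN) | Change | Low/Normal/High cell |
|---|---|---|
| 0.9 to 1.1 | +0.2 | Normal to High |
| 1.2 to 3.0 | +1.8 | High to High |
| 1.5 to 6 | +4.5 | High to High |
| 3.5 to 10 | +6.5 | High to High |

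The smallest change is the only one that registers as a shift.

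**Step 2: what the numerical summaries show for the 3.5 to 10 child.** The change is 10 - 3.5 = 6.5, and the mean change is 6.5/n.

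| n | Mean change (x ULN) | Median change | Q3 of change | Maximum change (x ULN) |
|---|---|---|---|---|
| 30 | 6.5/30 = 0.217 | 0 | 0 | 6.5 |
| 50 | 6.5/50 = 0.130 | 0 | 0 | 6.5 |
| 100 | 6.5/100 = 0.065 | 0 | 0 | 6.5 |

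The mean dilutes the event, and the median and upper quartile miss it. The maximum keeps it in full at every group size. A boxplot shows it if outliers are drawn.

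**Step 3: what remains missing.** The maximum is one number per group. It does not say how many children worsened, or where the extreme child started: a rise from 0.5 to 7 and a rise from 3.5 to 10 both give +6.5. The planned summaries are also not in ULN multiples, although testing is local in a two-country study. The listings carry values and ranges but no count. SAP 15.4 plans a separate listing of changes from baseline for vital signs; 15.3 names none for laboratory data.

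**The case against.** The strongest reply is that nothing is hidden. SAP 15.3 plans the maximum change, boxplots and range-flagged listings, and Protocol 9.4.2 lists every value. With one post-dose laboratory sample in a descriptive trial of 265 to 335 children, a medical reviewer could find the few cases directly. Section 8.2.4 requires the investigator to review each laboratory report and record clinically relevant changes. Appendix 3 allows a medically important laboratory abnormality to be reported as an adverse event, and Section 9.4.4 gives the IDMC all safety data at study end. The SAP also delivers the out-of-range shift tables that Protocol 9.4.2 calls for, so there is no contradiction. Section 8.2.1 reports no specific laboratory abnormality after praziquantel, and Section 4.2.6 expects few heavy *S. mansoni* infections.

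Most of this stands, and it rules out three stronger readings that a reader might infer:
- That worsening in these children appears nowhere. This is true only of the shift tables and category counts.
- That detection depends wholly on the investigator. The maximum and the full listings need no such judgement.
- That version 1.2 relaxed eligibility across the study. The criteria were removed from the Ivory Coast version to match Kenya, and exclusion 1 still applies in both countries.

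What the reply does not supply is a table. Listings and a single maximum let a reader find a case. They do not give the number of children already High who worsened, by treatment group and on a common scale.

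**Conclusion.** The point holds as a gap in the safety display. The SAP 15.3 shift tables and category counts cannot show liver worsening in a child High at baseline. No other planned table counts such children or expresses their change relative to the local ULN. The consequence is limited, because an individual case stays traceable through the maximum change and the listings.

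The number of children affected is not in the documents. Any figure would be an assumption: if 5% to 20% of the 100 children in group 1a were above range at baseline, 5 to 20 would have no upward shift available to them. That illustrates scale only and is not an estimate. It also counts every child above 1 x ULN, a wider group than those the removed Ivory Coast criteria described. Nothing here suggests that the treatment harms the liver or that the eligibility criteria are wrong; the documents support neither inference. The improvement is worth making because it is nearly free and lets a statement on hepatic safety be checked from the tables.

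**What to change.** In SAP 15.3, keep all existing displays and add the following for ALT, AST and total bilirubin:

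1. A derived variable, value divided by the ULN of the laboratory that ran the test, summarised at baseline, at 12 hours and as change. Table 7 says only bilirubin, so confirm that this is total bilirubin.
2. A baseline-by-12-hour shift table by treatment group in ULN-multiple bands, for example <=1, >1 to 3, >3 to 5 and >5 for ALT and AST, and <=1, >1 to 1.5 and >1.5 for bilirubin, with the number whose band worsens. The 3x and 1.5x points come from the removed Ivory Coast criteria and serve here as display categories only; the 5x point is an example.
3. A short listing, with both values in ULN multiples, of children above 3x (ALT or AST) or 1.5x (bilirubin) at baseline.

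Bands do not catch everything. Of the illustrated cases, 1.5 to 6 and 3.5 to 10 would now register, but 1.2 to 3.0 stays within >1 to 3, and the top band is open-ended. The summary in item 1 and the listing in item 3 cover part of that remainder.

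The cost is one derived variable, one shift table and a filtered listing, all from values and normal ranges already collected. No extra sampling is needed, and no change to eligibility or clinical management is proposed.

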15.4 Vital Signs

Vital signs including blood pressure (BP), pulse rate (PR) and body temperature will be assessed according to the trial schedule. Vital signs will be considered abnormal as follows:

| Parameter | Age | Low | Normal | High |
|------------------------------------|-----------------|-----|----------|------|
| Systolic blood pressure [mmHg]s | 3 - <12-months | <72 | 72 – 104 | >104 |
| | 12 - <24-months | <86 | 86 – 106 | >106 |
| | 2 - 6 years | <89 | 89 – 115 | >115 |
| Diastolic blood pressure [mmHg] | 3 - <12-month | <37 | 37 - 56 | >56 |
| | 12 - <24-months | <42 | 42 – 63 | >63 |
| | 2 - 6 years | <46 | 46 - 76 | >76 |

| Parameter | Age | Low | Normal | High |
|---------------------------|-------------------|-------|-------------|-------|
| Heart rate [beats/min] | 3 - <12-months | <100 | 100 - 180 | >180 |
| | 12 - <24-months | <90 | 90 - 160 | >160 |
| | 2 - 6 years | <80 | 80 - 140 | >140 |
| Oral Temperature [°C] | 3-month - 6 years | <35.5 | 35.5 - 37.5 | >37.5 |

Quantitative data will be summarized using descriptive statistics (mean, SD, median, Q1, Q3, minimum, and maximum) of actual values and changes from baseline to each visit over time.

Subjects data will be listed by cohort, subject and time point. An additional subject data listing will present all changes from baseline reported. Data will also be presented for absolute and change from baseline results using boxplots, by time point/visit.

15.5 Physical Examination

Physical examination will be done according to local procedures. Body weight will be recorded during the physical examination, i.e. at screening (before dosing) and 24 hours after dosing. Any abnormal physical examination findings will be presented as adverse events.

15.6 Tolerability Evaluations

The reaction to IMP administration (e.g. spitting, crying), tolerability, will be captured on the “Reactions to IMP/Biltricide® administration” eCRF pages. Data will be summarised through cross-tabulation with reaction category.

The palatability assessment will use a human gustatory sensation test (100-mm VAS) scoring modified by the incorporation of a 3-point facial hedonic scale for all children 5 and 6 years of age enrolled in the study.

Quantitative data will be summarized using descriptive statistics (mean, SD, median, Q1, Q3, minimum, and maximum, frequency and percentage) of palatability assessment.

Relevant data listings will be presented.

16 Analyses of Other Endpoints

16.1 Pharmacokinetics

To get information on systemic plasma concentrations after administration of L-PZQ ODT formulation in the targeted pediatric age groups, a subgroup of 20 participants 4 to 6 years of age (Treatment group 1a), 15 participants 2 to 3 years of age (Cohort 2), between 5 and 10 participants 3 to <24 months of age (Cohort 3), and 15 participants infected with *S. haematobium* (Cohort 4) are planned to supply blood samples for determination of systemic concentrations of R-Praziquantel, S-Praziquantel, R-4-OH-Trans Praziquantel and S-4-OH-Trans Praziquantel after treatment of L-PZQ 50 mg/kg. PK sampling from up to 15 participants in Treatment Group 1b will provide information on the systemic plasma concentrations

observed after Biltricide administration. An additional up to 15 participants will be collected for the 60 mg/kg dose group in Cohort 4b to study the systemic concentration of R-Praziquantel, S-Praziquantel, R-4-OH-Trans Praziquantel and S-4-OH-Trans Praziquantel after treatment of L-PZQ 60 mg/kg. A separate written informed consent will be obtained for PK sampling. Only participants with minimum hemoglobin of 10 g/dL will be asked to take part in the PK sub-study.

Blood samples of approximately 1 mL per time point will be collected for measurement of plasma concentrations of R-Praziquantel, S-Praziquantel, R-4-OH-Trans Praziquantel and S-4-OH-Trans Praziquantel, immediately prior to dosing (pre dose) and thereafter (post-dose), multiple times till 12 hours after dosing, as specified in the Schedule of Activities (Section 1.3 in protocol) and below. Instructions for the collection and handling of biological samples will be provided by the Sponsor. The actual date and time (24-hour clock time) of drug administration and each sample will be recorded in the eCRF.

Note: Analyses that took place prior to 01-Mar-2021 will only include R-Praziquantel and S-Praziquantel. All analyses taking place from 01-Mar-2021 will include 4 analytes R-Praziquantel, S-Praziquantel, R-4-OH-Trans Praziquantel and S-4-OH-Trans Praziquantel.

As the known variability of systemic PZQ concentrations and PK parameters is high in adults, the number of participants in each PK subgroup is not based on statistical considerations but on feasibility assessments. Children weighing 5 kg to less than 7 kg will have 4 PK samples taken, children weighing 7 kg to less than 10 kg will have 7 PK samples taken, and children weighing 10 kg and above will have the full PK sampling scheme with 9 PK samples taken. For background information please see “Appendix 6 (in protocol) Pharmacokinetic Blood Sampling”. Participants assigned to the PK sub study should fast between the dosing and 4h post dosing.

Table 1 PK sampling times per body weight group

| Body weight range (kg) | Sampling times (hours) | | | | | | | | | |
|------------------------|------------------------|-----------|---|---|---|---|---|---|----|---|
| | Pre dose | Post dose | | | | | | | | |
| 5 to < 7 | No | 0.5 | 1 | 2 | 3 | - | - | - | - | - |
| 7 to < 10 | No | 0.5 | 1 | 2 | 3 | 4 | 6 | 8 | - | - |
| 10 and above | Yes | 0.5 | 1 | 2 | 3 | 4 | 6 | 8 | 12 | |

Note: the tolerance window of $\pm 10\%$ for the collections of timepoints.

Plasma concentrations will be tabulated and summarized using descriptive statistics. PK parameters will be calculated if possible as appropriate for the respective sampling schemes. All PK parameters will be calculated using standard non compartmental methods and the actual administered dose. Calculations will be performed using a validated software tool as described below.

The following PK parameters will be calculated, when appropriate:

Table 2 PK parameters

| Symbol | Definition |
|------------------|--|
| C_{\max} | Maximum observed concentration in plasma |
| AUC_{0-t} | Area under the plasma concentration-time curve (AUC) from time zero to the last sampling time at which the concentration is at or above the lower limit of quantification. Calculated using the mixed log linear trapezoidal rule (linear up, log down). |
| t_{\max} | Time to reach the maximum plasma concentration |
| t_{lag} | Time prior to the first measurable (non-zero) concentration |

PK parameters will be evaluated and listed for all participants who provide sufficient concentration time data.

Estimation of Individual PK Parameters:

- Pharmacokinetic parameters will be calculated by the Clinical PK/PD Group of Translational Medicine, Merck, Darmstadt, Germany, or by a Contract Research Organization (CRO) selected by the Sponsor, using standard non-compartmental methods and the actual administered dose. PK parameters will be calculated using the actual elapsed time since dosing, given with a precision of 14 significant digits or the SAS format Best12. When the actual sampling time is missing, calculations will be performed using the scheduled time. Otherwise, there will be no further imputation of missing data.
- Non-compartmental computation of pharmacokinetic parameters will be performed using the computer program Phoenix® WinNonlin® version 6.3, or higher (Certara, L.P., [name]).
- The statistical software SAS® (Statistical Analysis System, SAS-Institute, Cary NC, USA, windows version 9.1 or higher) may be used to produce tables, listings and figures, if appropriate (see below). No other analyses are planned.

